12.1.2.2.2. Creatine Kinase Elevations

Refer to Section 7.3.1 for details on study drug discontinuation procedures related to elevated CK results.

The participant should be questioned about symptoms (eg, muscle or tendinous pain, cramping, or weakness) and potential causes for the CK elevation (eg, medications, exercise, or trauma). The following laboratory measurements should be obtained: CK, CK-MB, CK-MM, troponin, creatinine, myoglobin (serum and urine), transaminases, total bilirubin, and urinalysis including urine sediment. A physical examination should be performed, documenting findings such as muscle tenderness, weakness, or rash. An ECG should be collected as well. This information should be collected on the appropriate eCRF.

Confidential K-877-302 Study Protocol

Version 3 dated 18-Mar-2020

Abnormalities should be followed until they have returned to baseline, or the investigator considers them clinically stable.

12.1.3. Pregnancy Screen

Serum pregnancy testing will occur at the Screening/Enrollment Visit (Visit 1), Randomization (Visit 2), Month 2 (Visit 4), Month 4 (Visit 5), Month 6 (Visit 6), Month 12 (Visit 9), and at subsequent in-person visits including the CSED for all WOCP.

12.2. Adverse and Serious Adverse Events

12.2.1. Definition of Adverse Events

12.2.1.1. Adverse Events

An AE is any untoward or unfavorable medical occurrence in a human participant, including any abnormal sign (for example, abnormal physical exam or laboratory finding), symptom, or disease, temporally associated with the participant's participation in the research, whether or not considered related to the participant's participation in the research.

Any medical condition that is present at the time the participant is consented but does not deteriorate should not be reported as an AE. However, if it deteriorates or worsens significantly at any time during the study, it should be recorded as an AE.

12.2.1.2. Serious Adverse Events

An adverse event is categorized as serious if it:

- results in death
- is life-threatening
- requires inpatient hospitalization OR prolongs an existing hospitalization
- is associated with a persistent or significant disability or incapacity or with a congenital anomaly or birth defect, or
- is a medically significant event, as determined by the Principal Investigator, even if it does not meet any of the other criteria for seriousness

Death is considered an outcome of an adverse event, and as such, the cause of death should be recorded as the adverse event. 'Death' should not be reported as an event term unless the cause of death is unknown at the time of reporting. If 'death' is reported as an event, the investigator should update the event term to the cause of death when this information becomes available.

Life threatening: An adverse event is considered 'life-threatening' if, in the view of either the investigator or Sponsor, its occurrence places the participant at immediate risk of death. It does not include an adverse event that, had it occurred in a more severe form, might have caused death.

Hospitalization or prolongation of hospitalization: Kowa considers 'hospitalization' as admission to a hospital for any inpatient care, or an emergency room stay with a duration of 24 hours or longer. The definition of hospitalization does not include:

- an emergency room visit for less than 24 hours or admission to an outpatient facility
- a hospitalization that was elective or pre-planned for a pre-existing condition and not related to worsening of an underlying condition
- a hospitalization for social reasons and not related to a change in the participant's general condition

Medically significant/important medical event: An important medical event that may not be immediately life-threatening or result in death or hospitalization, but based on medical judgment may jeopardize the participant and may require medical or surgical intervention to prevent any of the outcomes listed above (ie, death, life-threatening, hospitalization, prolongation of hospitalization, persistent or significant disability/incapacity or congenital anomaly).

12.2.2. Adverse Event Severity

The intensity of the AE will be rated by the investigator as mild, moderate, or severe using the following criteria:

Mild: an event that is transient and easily tolerated by the participant, requires minimal or no treatment, and does not interfere with the participant's daily activities.

Moderate: an event that causes the participant discomfort and may cause some interference in the participant's usual activities.

Severe: an event that causes considerable interference with the participant's usual activities, may require drug therapy or other treatment.

12.2.3. Relationship to Study Drug

An investigator who is qualified in medicine must make the determination of relationship to the investigational product for each AE. The investigator should decide whether, in his or her medical judgment, there is a reasonable possibility that the event may have been caused by the investigational product. If no valid reason exists for suggesting a relationship, then the AE should be classified as "unrelated." If there is any valid reason, even if undetermined, for suspecting a possible cause-and-effect relationship between the investigational product and the occurrence of the AE, then the AE should be considered "related."

The following guidance should be used by investigators when assessing relationship:

Related:

• Occurs within a reasonable temporal sequence to administration of study drug

- Cannot be explained by concurrent disease or other drugs or chemicals
- Improves or disappears on stopping or reducing study drug (de-challenge)
- Reappears on repeated exposure to study drug (re-challenge)
- Is an unusual event that is known to be associated with the drug or this class of compound, and cannot be explained by other therapy or the participant's physical condition
- Unlikely to be attributed to concurrent disease or other drugs or a clinically reasonable response on withdrawal (de-challenge)

Unrelated:

- Occurs with a temporal relationship to administration of study drug which makes a causal relationship improbable
- Other drugs, chemicals or underlying disease provide plausible explanations of causality
- Is known to be associated with the participant's clinical condition, or with other medication taken by the participant

12.2.4. Action Taken Due to AE

The following are actions taken to treat the AE and actions taken on study treatment as a result of the AE, and must be recorded in the event of an AE:

Action taken to treat the AE

- None
- Treatment required
- Hospitalization
- Participant withdrawn
- Other (specify)

Action taken with study treatment

- Drug interrupted
- Drug withdrawn
- Not applicable, or

Unknown

12.2.5. Adverse Event Outcomes

The following are AE outcomes, and must be recorded in the event of an AE:

- Resolved: The event has recovered
 - Note: An SAE/AE stop date should be provided
- Resolved with sequelae: The study participant has recovered as much as may be expected but is left with sequelae of the event that are not expected to recover further
 - Note: If the sequelae are severe enough to represent a significant disability or incapacity then the event should be reported as an SAE
- Resolving: Can be used in cases where study participant is known to be clearly recovering from the event at the end of a study, although the event is not yet resolved, and the investigator and Medical Monitor agree that further follow-up is not necessary
- Death: The study participant died as a result of the AE
 - Note: Death is considered an outcome of an AE rather than an AE in its own right, and the cause of death should be recorded as the AE. There may be rare circumstances where the cause of death is unknown and the death may have to be recorded as the event (eg, "sudden cardiac death"). Adverse events resulting in death are SAEs
- Not resolved: The participant has an AE that has not improved or recuperated at the time of the report, or
 - o Note: The decision not to continue follow-up should be discussed between the investigator and Medical Monitor and recorded in the source documents
- Unknown: The outcome of the event is genuinely unknown in spite of efforts to contact the participant.

12.2.6. Adverse Event Collection Period

The SAE reporting period for safety surveillance begins when the participant is initially included in the study (date of first signature of informed consent) and will continue until the Post-Study safety call, 30 days after the CSED Visit. Adverse events occurring prior to and inclusive of the randomization visit and following the CSED Visit will comprise SAEs only; otherwise, all AEs will be recorded.

12.2.7. Adverse Events of Special Interest

Adverse events of particular interest as they pertain to pemafibrate will include muscle-related AEs and liver disease. Adverse event forms will be used to collect additional relevant clinical

information at each study visit at which AEs will be assessed. Instructions for entry of these events will be provided in the eCRF Completion Guidelines.

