4.8. Benefit-Risk Assessment

The overall drug profile outlined in Section 4.7 is favorable for human studies at chronic doses up to 0.4 mg/day. The maximum dose administered in a single-dose study was 1.6 mg and the maximum dose for 1-week of treatment was 1.6 mg/day; both regimens were well tolerated. In patients with dyslipidemia, a maximum dose of 0.4 mg/day was well tolerated for up to 52 weeks.

As with all drugs, the potential for hypersensitivity and allergic reactions has to be taken into consideration when pemafibrate is administered. Other risks to the patients are the risks inherent to any clinical study with an unapproved drug such as unexpected adverse clinical or laboratory events.

Because of the mechanism of action, 2 important potential risks are identified. Since other fibrates have been shown to increase the risk for cholelithiasis, pemafibrate could also increase the risk of cholelithiasis. Other fibrates have been shown to increase the risk for rhabdomyolysis when co-administered with statins. Rhabdomyolysis has not been reported with the use of pemafibrate, and no difference has been observed in the incidence of musculoskeletal-related AEs between patients with and without co-administered statins. Although rare, the risk of rhabdomyolysis cannot be excluded when pemafibrate is co-administered with statins, especially in patients with severe renal impairment, as there is limited experience to date with the combined use of pemafibrate and statins in such patients. In this study, patients with severe renal impairment will be excluded from participation.

Other potential risks include elevated transaminases (ALT, AST), decreases in red blood cell (RBC) count and hemoglobin, and musculoskeletal and connective tissue disorders (eg, myopathy, myalgia, and increased creatine kinase [CK]).

Because of significant increases in plasma concentrations of pemafibrate in patients with severe hepatic disorders, patients with liver disease will be excluded from the study. Concomitant use of cyclosporine, rifampicin, or other OATP inhibitors will be prohibited in the study (Section 8.2), as co-administration of pemafibrate with cyclosporine and single doses of rifampicin have resulted in increases in pemafibrate exposure due to inhibition of OATP1B1 or OATP1B3 by these drugs.

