In addition to the above, an analysis of time to first occurrence of individual endpoints and an analysis of total events (evaluating time to occurrence of the first and all recurrent non-fatal MI, nonfatal ischemic stroke, coronary revascularization, or CV death) will be performed.

Additionally, as a prespecified secondary analysis, evidence of any genetic effect modification that may relate to pemafibrate and incident CV events will be evaluated. In particular, whether the effect of pemafibrate as compared with placebo on CV events differs according to known genetic polymorphisms in the PPAR- α gene (such as, but not limited to rs6008845) will be assessed.

Safety Analyses:

The safety population includes all participants who received at least 1 dose of study treatment. Participants will be analyzed according to their randomized treatment group, unless a participant inadvertently receives the incorrect drug during the entire study, in which case, the participant will be grouped according to the treatment actually received. Safety analyses will include comparisons of post-randomization laboratory values by treatment group and rates of SAEs and AEs by treatment group, both overall and within system organ class (SOC).

October 24, 2022

Planned Interim Analyses:

To preserve alpha and to minimize the likelihood of an inflated effect estimate associated with early stopping, preplanned efficacy analyses will occur only upon accrual of approximately 50% and 75% of the planned study primary endpoints. The design of the study, including evaluation of the implications of interim monitoring on study power, considered that stopping boundaries will be based on the Haybittle-Peto method. Inefficacy will be assessed at 30%, 50%, and 75% of endpoints, based upon the Linear 10% Inefficacy Boundary approach described by Freidlin, Korn, and Gray.

TABLE OF CONTENTS

1.	LIST OF ABBREVIATIONS	21
2.	INTRODUCTION	24
3.	STUDY OBJECTIVES AND ENDPOINTS	25
3.1.	Study Objectives	25
3.1.1.	Primary Objective	25
3.1.2.	Secondary Objectives	26
3.1.3.	Tertiary Objectives	26
3.2.	Study Endpoints	26
3.2.1.	Primary Endpoint	26
3.2.2.	Secondary Endpoints	26
3.2.3.	Tertiary Endpoints	27
4.	STUDY DESIGN	29
4.1.	Summary of Study Design	29
4.2.	Definition of Study Drugs	32
4.3.	Sample Size Considerations	32
4.3.1.	Sample Size Justifications	32
4.3.2.	Sample Size Re-estimation	34
4.4.	Randomization	34
4.5.	Clinical Assessments	35
5.	PLANNED ANALYSES	39

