10.2.1. Summaries of Adverse Event Incidence Rates for All Subjects

Incidence of TEAEs will be presented by SOC and PT. Subjects will be counted only once at the SOC level and will be counted once for each applicable PT; multiple occurrences of the same preferred term for a subject will be counted only once. Subjects who experience more than one event within the same SOC are counted once at each preferred term level.

Supplementary tables will summarize the events with respect to the maximum severity observed for each preferred term and relationship to study medication.

10.2.2. Summaries of Adverse Incidence Rates for Serious Adverse Events (SAE), Adverse Event Dropouts, and Death

Adverse event incidence rates, by SOC and PT, will be summarized for subjects who report a non-fatal serious adverse event, discontinue treatment prematurely due to an adverse event, and

deaths. A listing will also be generated of premature discontinuations due to all causality. Individual data listings will support these tables in two forms:

- 1. Sorted by subject and all events at the preferred term level.
- 2. Sorted by preferred term and listing all subjects.

10.3. Total Duration of Therapy, Average Daily Dose, Maximum Daily Dose, Final Daily Dose of Study Medication, Compliance, and Study Drug Exposure

The duration of treatment will be summarized as a continuous measure and in a frequency distribution. The average daily dose, maximum daily dose attained at any time during the study, the final daily dose taken just prior to study termination, and compliance will also be summarized.

Subject months of drug exposure will be presented as cumulative summary statistics. The total number of days of treatment will be determined for each subject and then summed over all subjects. This total is divided by 30 days to estimate the months.

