10.5. Routine Laboratory Data

Results from the central laboratory will be included in the reporting of this study for Hematology, Blood Chemistry and Urinalysis. Presentations will use SI units. Tryglicerides and Glucose will be split by fasting status. An additional by visit Lipid table will be presented using conventional units along with the reference ranges and change from baseline.

Quantitative laboratory measurements reported as "< X", i.e. below the lower limit of quantification (BLQ), or "> X", i.e. above the upper limit of quantification (ULQ), will be converted to X for the purpose of quantitative summaries.

Actual and change from baseline by visit will be summarized for quantitative measurements. The within-group p-value from the paired t-test on the mean change from baseline and the 95% confidence interval limits for the mean change from baseline are also included with the change descriptive statistics. For select quantitative laboratory data, assessments will also be presented graphically to show the change from baseline as a function of the baseline value.

Shift tables (in categories of low, normal, and high) from baseline to each post-baseline scheduled visit will be provided by treatment group for selected laboratory parameters. Also, the number and percentage of subjects with clinically relevant abnormal laboratory values will be

calculated for each treatment group for selected laboratory parameters. Percentages for these summaries will be based on the available data, rather than the total number of subjects.

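### SAP Section 10 gives no drug-versus-placebo estimate for laboratory change and fixes no muscle, hepatic or gallstone groupings, although the protocol names these risks

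*Protocol*

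**What the plan says.** **The risks named in advance.** Protocol 4.8: "Because of the mechanism of action, 2 important potential risks are identified". The first is gallstones: "Since other fibrates have been shown to increase the risk for cholelithiasis, pemafibrate could also increase the risk of cholelithiasis". The second is rhabdomyolysis when a fibrate is given with a statin. The same section lists raised transaminases and muscle disorders as further potential risks. Protocol 12.2.7: "Adverse events of particular interest as they pertain to pemafibrate will include muscle-related AEs and liver disease". That section provides for collecting extra clinical information on these events.

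**The adverse event tables.** SAP 10.1 gives the number and percentage of subjects in broad categories of treatment-emergent event. SAP 10.2.1: "Incidence of TEAEs will be presented by SOC and PT", with further tables by maximum severity and by relationship. Its counting rule is: "Subjects who experience more than one event within the same SOC are counted once at each preferred term level". SAP 10.2.2 adds tables for non-fatal serious events, discontinuations and deaths, supported by subject-level listings.

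**The laboratory and vital-sign tables.** SAP 10.5 attaches this to each change from baseline: "The within-group p-value from the paired t-test on the mean change from baseline", with a 95% CI for the mean change. It plans shift tables and says that "the number and percentage of subjects with clinically relevant abnormal laboratory values will be" given for each arm, without naming parameters or limits. SAP 10.6 organizes vital signs in the same way.

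**The summary.** The SAP's Technical Summary promises more: "Safety analyses will include comparisons of post-randomization laboratory values by treatment group and rates of SAEs and AEs by treatment group". It names no estimator, interval or grouping below SOC.

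**The concern.** The safety question in a placebo-controlled trial is drug against placebo. Section 10 puts the arms side by side, but the only p-values and intervals it specifies compare each arm with its own baseline. In a large trial these respond to very small drifts from ageing, background therapy, assay change or regression to the mean. A p-value below 0.05 in one arm and above it in the other is easily taken for a drug effect.

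For the pre-named harms, no row counts participants with any muscle, hepatic or gallstone event. A subject with two related terms appears in two PT rows, so the rows cannot be summed to participants, and an SOC row also holds unrelated events. If a grouped count is built later, its terms are chosen with the arms known. That invites doubt about the choice, whichever way the result falls.

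**Working it through.** The documents state no figure for any safety comparison, so there is none to reproduce. The one design input used is 5,000 per arm (Protocol 14.2); 4,000 per arm shows the effect of missing data. Drift sizes and event incidences are assumptions, because the documents give none.

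**1. What the within-arm test responds to.** With drift in SD units of the change, the smallest drift giving two-sided p < 0.05 is 1.96/√n.
- n = 5,000: 1.96/70.71 = 0.028 SD
- n = 4,000: 1.96/63.25 = 0.031 SD

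The between-arm 95% CI half-width is 1.96 × √(2/n): 0.039 SD and 0.044 SD.

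**2. Equal drift d in both arms, so no drug effect.** P(one given arm significant) = pw = P(|Z + d√n| > 1.96). P(exactly one arm significant) = 2 × pw × (1 − pw).

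| d (SD) | n = 5,000 | n = 4,000 |
|---|---|---|
| 0.02 | 41% | 37% |
| 0.028 | 50% | 49% |
| 0.05 | 11% | 20% |

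For d = 0.02 and n = 5,000: d√n = 1.41, pw = 0.293, and 2 × 0.293 × 0.707 = 0.414. A between-arm test holds its false-positive rate at 5% for any common drift.

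**3. Worked example, n = 5,000.** One arm drifts +0.035 SD (z = 2.47, p = 0.013), the other +0.020 SD (z = 1.41, p = 0.16). The difference is 0.015 ± 0.039, so the 95% CI is −0.024 to 0.054 (p = 0.45).

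**4. Grouped row against single rows (illustration only).** Risk ratio CI = exp(ln RR ± 1.96 × √[(1−p1)/(n p1) + (1−p2)/(n p2)]), n = 5,000, placebo p1 and pemafibrate p2. The true group ratio is 1.50.

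| Row reported | Group 1.0% vs 1.5% | Group 2.0% vs 3.0% |
|---|---|---|
| Whole group | 1.50 (1.05–2.14) | 1.50 (1.17–1.93) |
| PT with 80% of those affected | 1.50 (1.01–2.23) | 1.50 (1.13–1.98) |
| PT with 50% | 1.50 (0.91–2.48) | 1.50 (1.05–2.14) |
| PT with 20% | 1.50 (0.67–3.34) | 1.50 (0.85–2.64) |
| SOC, plus 1% other subjects per arm | 1.25 (0.96–1.62) | 1.33 (1.08–1.64) |
| SOC, plus 5% other subjects per arm | 1.08 (0.93–1.26) | 1.14 (0.996–1.31) |

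The SOC rows assume no overlap between the group and the other subjects. If one PT holds everyone affected, grouping adds nothing.

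**5. Adding PT rows is not a substitute.** Take 50 placebo and 75 pemafibrate participants.
- Two terms each: the sums are 100 vs 150, giving a CI of 1.17–1.93 where the participant count gives 1.05–2.14.
- 1.2 terms per placebo and 1.4 per pemafibrate participant: the sums are 60 vs 105, a ratio of 1.75 where the participant ratio is 1.50.

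**The case against.** Several points on the other side stand.

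- **Listings.** A reader might infer that grouped counts can never be recovered. The documents do not support that. SAP 10.2.2 plans listings sorted by subject and by preferred term, and SAP 6.1 plans supportive subject listings by treatment group. Unique participants could be counted from these. The 10.2.2 listings support the serious-event, discontinuation and death tables, so their coverage of non-serious events is uncertain. The lasting issue is when the terms are chosen.
- **Hand calculation.** Per-arm means, SDs and counts allow a between-arm estimate to be worked out for any printed row. What is missing is the pre-specified column.
- **Use of the p-values.** Nothing in the SAP says that within-arm p-values will be read as drug effects. The figures in steps 2 and 3 show what such a reading would cost. Liver and muscle harm would also tend to appear as outliers, for which shift tables and abnormal counts by arm are planned.
- **No broken commitment.** A reader might infer a conflict between protocol and SAP. Section 12.2.7 commits to collecting data, and side-by-side tables could satisfy the summary's promise of comparisons.
- **Unseen material.** SAP 5.2 refers to a full set of output templates. These, or the DSMB charter, may define groupings.

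Descriptive safety tables are also a legitimate way to limit unadjusted inference. But Section 10 already specifies p-values, and they address change from baseline.

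**Conclusion.** The point holds for the SAP text as a low-cost improvement. Section 10's only stated inference is within-arm and does not address drug versus placebo, and no muscle, hepatic or gallstone grouping is fixed, although the protocol names these risks.

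The laboratory arithmetic needs only the planned arm size and assumed drifts of 0.02 to 0.05 SD. At 5,000 per arm, the chance of a one-arm-only significant result with no drug effect is 11% to 50%. The adverse event figures rest wholly on assumed incidences and term shares. The gain from grouping runs from nil, when one term dominates, to a change in whether the interval excludes 1.

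It would go too far to say that a harm will be missed. Earlier transaminase events were more frequent than on placebo but less so than on fenofibrate (Protocol 4.7.2), and rhabdomyolysis had not been reported (Protocol 4.8). The primary efficacy conclusion is unaffected.

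**What to change.** Before unblinding:

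1. **SAP 10.5 and 10.6.** Add between-arm differences in mean change with 95% CIs, beside or in place of the within-arm p-values.
2. **SAP 10.2.** Fix three MedDRA groupings (standard queries or listed terms, with the dictionary version):
   - gallstone/biliary, starting from cholelithiasis;
   - muscle, starting from the Protocol 4.8 terms (rhabdomyolysis, myopathy, myalgia, CK increase);
   - hepatic, starting from the Protocol 4.7.2 terms (abnormal liver function test, ALT or AST increase).
3. **For each grouping.** Report participants with a first event by arm, and a rate ratio or risk difference with 95% CI, labelled as an unadjusted safety estimate. If rates are used, count person-time from first dose to the first event in the group or 30 days after last dose, ending earlier at death or last contact. This matches the treatment-emergent window in SAP 10.1.
4. **Minor clarification.** Cross-reference the Protocol 7.3.1 limits for the abnormal-value counts: ALT or AST above 3 and above 8 times the upper limit of normal (ULN), ALT or AST above 3 times with bilirubin above 2 times ULN, and CK above 5 and above 10 times ULN.

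If the output templates already contain this, a citation in Section 10 is enough.

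The cost is SAP wording, medical review of three term lists, three tables and one column of differences. The data are already being collected and no protocol amendment is needed. The downside is a few more unadjusted safety comparisons.
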